[figure not shown]
II. Study design

This is a pilot study that will evaluate the feasibility of a home-based approach to influenza infection for households in the Seattle, WA area, utilizing an influenza self-test, followed by telehealth consultation for diagnosis and rapid home delivery of antivirals. Households with 3 or more of the same members at least 4 days per calendar week will be eligible to enroll, as long as there are at least 2 members in household eligible to take BXM. Individuals 12 years or older, weighing at least 40 kg, will eligible to take BXM, and thus, are able to enroll as drug eligible participants. Individuals that are not able to take BXM will be able to enroll in the study as drug ineligible participants. Individuals within an eligible household will be enrolled prior to or during the annual influenza season and monitored throughout the influenza season for the development of a cough or 2 or more respiratory symptoms. If a drug ineligible study participant, meaning a household member who does not meet BXM criteria, develops symptoms, they will use an influenza self-test; however, regardless of the result, they will not be able to receive BXM. Nevertheless, the drug ineligible study participant will provide one self-collected or parent/permanent legal guardian-collected nasal swab specimen that will be mailed back to the laboratory for further testing.

If a drug eligible study participant in the household develops a cough or 2 or more respiratory symptoms, he/she will use a prepositioned influenza self-test kit as soon as possible. Additionally, the individual will connect with a healthcare provider through the 98point6 app to

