SFS Statistical Analysis Plan
Household Intervention Study
Last Revised 10/8/19

Applicable to the following UW IRB Study Protocols:

Seattle Flu Study (SFS) **(6181)**

Household Intervention Study **(8200)**

Funding:

Brotman-Baty Institute, University of Washington

Table of Contents

A. STUDY OBJECTIVES AND SUMMARY	3
B. FINAL ANALYSIS PLAN	4
B1. ANALYSIS DATASETS	4
B2. BASELINE TABLES AND STUDY CONDUCT	5
Description of the main tables and statistical analyses	5
Study Accrual	5
Baseline Demographic Characteristics	5
Baseline Behavioral Characteristics	5
Baseline Influenza and Respiratory Illness Symptoms	5
Drug adherence	5
Retention	5
Follow-up	5
B3. SAFETY ANALYSIS	5
B4. ENDPOINT ANALYSIS	5
Primary Analysis	5
Secondary Analyses	5
Additional analyses with Influenza virus infection as the Endpoint	5
Additional analyses with other respiratory infections as Endpoints	5
Sensitivity Analyses	5
C1. INTERIM ANALYSIS PLAN	5
Original plan	5

A. Study Objectives and Summary

Purpose: To evaluate the efficacy of a home-based approach to influenza testing in households in order to shorten the time to diagnosis, antiviral delivery, and antiviral initiation and reduce influenza transmission within the household.

Design: This study is an open cohort intervention study with prospective exposure assessment. It is a pilot study of a home-based approach to influenza infection, utilizing self-test kits and rapid home delivery of baloxavir (BXM). All members of all households must be asymptomatic at enrollment.

Population: Households with at least 3 individuals residing there at least 4 days a week, including at least 2 household members that are eligible to take BXM, will be monitored throughout the influenza season for the onset of a cough.

Expected study size: This study will be conducted in up to 1,000 households in the Seattle, WA area.

Study duration: One influenza season, beginning November 1, 2019 and ending May 1, 2020.

Primary aim: Evaluate whether this home-based strategy leads to a large percentage of influenza-positive individuals initiating antiviral therapy within 48 hours of symptom onset.

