A list of serious adverse events will be presented by shelter and by treatment v. intervention period. As defined in the study protocol, serious adverse events include death, a life-threatening reaction to the study drug (or placebo) or other study procedure, hospitalization, or significant or persistent disability or impairment. The incidence of SAE's (events/person-days of follow-up) will be presented both (1) overall and (2) by case v. non-cases. We will test for a difference in SAE rate between the two study periods (intervention v. control) using an exact Poisson test in R.

Baloxavir-resistant influenza transmission

Evidence of a strong intervention effect causing incidence of baloxavir-resistant influenza strains will be evaluated using linear mixed effects logistic regression. The unit of analysis will be influenza-positive tests, and the outcome will be binary: baloxavir-resistant or not baloxavir-resistant.

B5. Power sample size

Table 1. Sample size calculations: Number of clusters needed per arm for two-group cluster-randomized trial - Household intervention study

Effect size (% reduction in flu incidence)			
Power	0.30	0.40	0.50
0.80	57	84	129
0.90	76	112	172

All calculations above assume an ICC of 0.29, anticipated average (or actual) cluster size of 4, and a 15% transmission rate for flu.

Based on these calculations, an arm size of 250 households should be sufficient to detect a 30% reduction in flu incidence at 90% power.

B6. Endpoint Analyses

Primary Analysis

[figure not shown]
Question: Does this home-based self-test diagnostic tool and rapid treatment intervention lead to a large percentage of influenza-positive individuals initiating antiviral therapy within 48 hours of symptom onset?

Endpoint: Cumulative incidence of influenza virus infection

Measure of Association:
Cumulative Incidence (Attack Rate, Incidence Proportion)

$$\text{Cumulative Incidence} = \frac{\text{Number of participants that successfully initiate antiviral therapy within 48 hours of symptom onset (among participants who have a cough and self-test positive for influenza) during the October 2019-May 2020 influenza season}}{\text{Number of influenza-free participants at risk at } t_0 \text{ (baseline)}}$$

Relevant DAG

Exposure:

Exposed (Treatment) = Participants who develop cough and self-test positive
Unexposed (No treatment) = Participants who develop cough but self-test negative

Outcome:

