Success = Participant initiated on antiviral therapy within 48 hours of symptom onset
Failure = Participant is not initiated on antiviral therapy (**more than 48 hours** after symptom onset *or* participant **never** initiates antiviral therapy)

Table 1. Estimated secondary attack rates for planned 2019-2020 study aim on household transmission dynamics.

The study is being conducted in the Seattle, WA area over one influenza season. The goal is to enroll at least 250 (up to 1,000) households. Of these, 25% are estimated to have an individual in the household diagnosed with influenza based on estimates from previous household studies.^{23, 28-29}

A table for influenza attack rates by household size is provided below.

Household attack rate	Total households enrolled	Primary cases	Secondary cases (mean household size 5)	Secondary cases (mean household size 4)	Secondary cases (mean household size 3)
25%	250	63	45-96	34-72	23-48

20%	250	50	36-76	27-57	18-38
10%	250	25	18-38	14-29	9-19
Mean household size includes case.					
Secondary attack rate 18-38%, secondary cases presented as a range based on these high and low bounds.³⁰⁻³²					

Incidence Density

Using time-specific variables such as date of enrollment, weekly symptom diaries and questionnaires, Incidence Density (ID) will be calculated, defined with the following formula:

Incidence Density =

Number of participants that successfully initiate antiviral therapy within 48 hours of symptom onset (among participants who have a cough and self-test positive for influenza)

Total person-days

Model

The proportion of individuals that 1) test positive and 2) receive and initiate treatment within 48 hours of symptom onset using home-based self-test and delivery methods will be analyzed with a binomial regression GLMM with a log link. The outcome follows a binomial distribution, with the number of successes in a series of n independent Bernoulli trials, where each trial has probability of success p . Successes here are defined as an individual successfully initiated on antiviral therapy within 48 hours of symptom onset using home-based self-test to diagnose influenza and home delivery of antivirals. The model is defined below:

Incidence proportions of influenza will be presented in tables.

A formal statistical comparisons between study periods (control vs. intervention) will be performed using a Wald test of the hypothesis

$H_0: RR=1$

$H_a: RR \neq 1$

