Question: Does influenza incidence change when we look at varying testing timepoints (e.g. testing within 24, 48, and 72 hours of symptom onset)?

Details:

A sensitivity analysis will be performed to assess the effect of delayed testing on the intervention effect. The model will be re-run with three subsets of the data: those that were treated within 24, 48, and 72 hours of symptom onset. This will then be further analyzed with a time*age interaction. For example, we might expect that a 13-year-old might have more detectable RNA virus than an older adult at the same time point.

Data cleaning and software

All analyses will be performed in R version 3.6.1 using packages `'lme4'` and `'swCRTdesign'`.

C. Interim Analysis Plan

Original Plan

The DSMB will meet every month to review study progress and other issues as outlined below. In the proposed 6 month study, it is expected that the DSMB will meet X times.

Study progress and validity

At each monthly visit the DSMB will review data on enrollment, adherence of both households and household members, and all protocol violations. The DSMB will also compare the (pooled) observed influenza incidence rate to the (pooled) expected influenza rate to determine if the influenza incidence rate among study participants is at least as great as the incidence rate assumed in the study design, since incidence varies by influenza season. The DSMB will recommend any changes to the study design they believe are needed to ensure study validity.

Expected event rate: 150/1000 pdy in the control period and 120/1000 pdy in the intervention period; 135/1000 pdy overall.

Efficacy monitoring

Baloxavir-resistant influenza strain transmission

Additional testing and sequencing of non-influenza respiratory pathogens will also occur. Baloxavir resistance will be analyzed via interim analyses and monitored for the duration of the study. In the unlikely event that the incidence of the transmission of baloxavir-resistant strains of flu exceeds 20% of study participants, the study will be halted.

Tables and Figures

Table 1a. Sociodemographic characteristics of individual participants, SFS Household Intervention Study, 2019-2020 influenza season

Variable	Full sample n=	Cases only n=
Sociodemographic variables		
Age - median (range)		
Sex		
Male		
Female		
Race		
American Indian or Alaska Native		
Native Hawaiian or other Pacific Islander		
Black or African American		
White		
Multiple Races		
Other		
Prefer not to say		

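### The SAP's DSMB incidence benchmark of 135/1000 pdy rests on control and intervention periods this single cohort does not have, and its unit is undefined, so the check can pass or fail depending on how it is read

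*SAP*

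**What the plan says.** SAP section C (Interim Analysis Plan, Study progress and validity) asks the DSMB, at monthly meetings, to "compare the (pooled) observed influenza incidence rate to the (pooled) expected influenza rate". The purpose is to "determine if the influenza incidence rate among study participants is at least as great as the incidence rate assumed in the study design". The benchmark supplied is "Expected event rate: 150/1000 pdy in the control period and 120/1000 pdy in the intervention period; 135/1000 pdy overall". On what follows from the check, the SAP says: "The DSMB will recommend any changes to the study design they believe are needed to ensure study validity".

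The design is described differently. SAP section A states: "This study is an open cohort intervention study with prospective exposure assessment". Protocol section II states: "This is a pilot study that will evaluate the feasibility of a home-based approach to influenza infection for households in the Seattle, WA area". Neither describes a control arm or a control period.

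The planning figures appear in Protocol section II and again in SAP B6. Of 250 households, "25% are estimated to have an individual in the household diagnosed with influenza", which the table shows as 63 primary cases, with secondary cases at 18–38% of remaining members for mean household sizes 3, 4 and 5. Protocol section XI uses the same 63 for its ±0.12 precision statement.

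SAP B5 is separate: a two-arm cluster-randomised calculation with a 15% transmission rate, concluding that "an arm size of 250 households should be sufficient to detect a 30% reduction in flu incidence".

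**The concern.** The benchmark has a job: it is the yardstick by which the DSMB judges whether the season is producing enough influenza for the study to remain valid, and the DSMB may recommend design changes on the result. A yardstick that averages two periods, one of which does not exist, cannot be compared with a pooled observed rate from one cohort. If its unit is also unclear, two competent readers can reach opposite answers from the same data. At stake is either false reassurance in a season below the planning assumption, or a needless recommendation to change a season that is on plan.

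**Working it through.** **Inputs.** 150, 120 and 135 per 1000 *pdy* (SAP C). 250 households, 25% attack rate, 63 primary cases, secondary attack rate 18–38%, household sizes 3–5 (Protocol II, SAP B6). Season 1 November 2019 to 1 May 2020, which is 182 days (SAP A). Assumption: everyone is followed for all 182 days.

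**The plan's own figures.** (150 + 120)/2 = 135, so the overall rate reproduces, but only with half the person-time in each period. The planning table also reproduces: primary = 250 × 0.25 = 62.5, shown as 63; secondary = 63 × (size − 1) × 0.18 to 0.38. At size 4 that is 34.0 to 71.8, matching the printed 34–72.

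**What the planning figures imply.** Incidence per 1,000 people per season = 1,000 × (primary + secondary)/(250 × size). Multiply by 365/182 for person-years; divide by 182 for person-days. Size 4, lower bound: (63 + 34.0)/1,000 gives 97 per 1,000 per season; × 365/182 = 195; 97/182 = 0.53.

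| Household size | All infections, per 1,000 people per season | All infections, per 1,000 person-years | All infections, per 1,000 person-days | Primary cases only, per 1,000 person-years |
|---|---|---|---|---|
| 3 | 114–148 | 229–296 | 0.63–0.81 | 168 |
| 4 | 97–135 | 195–270 | 0.53–0.74 | 126 |
| 5 | 87–127 | 174–255 | 0.48–0.70 | 101 |

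**Placing 135 against these, by reading of the unit.**

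- *Person-days*, the only person-time unit the SAP spells out (SAE incidence in B4, incidence density in B6): 0.135 × 182 = 24.6 infections per person per season. This is impossible.
- *Person-years, all infections*: 135 × 182/365 = 67 per 1,000 people per season, against 87–148 planned. As rates, 135/296 = 46% and 135/174 = 78% of plan.
- *Person-years, primary cases only*: planned 101–168, and 126 at size 4. 135 is compatible.
- *Seasonal cumulative per 1,000 people*: 135 equals the top of the size 4 range (63 + 72 = 135), lies inside size 3 and is above size 5.

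**The same season under different readings.** Take a season exactly on plan at size 4 with a mid-range secondary attack rate of 28%: 63 + 63 × 3 × 0.28 = 116 infections per 1,000 people. Read per season, 116 is below 135 and the check fails. Read per person-year, 116 × 365/182 = 232 is above 135 and the check passes. Now take the table's 20% attack-rate row, below the planning assumption. Per person-year its all-infection rate is 138–235 across sizes 3–5, so it passes at every size. Per season it is 69–117, so it fails at every size.

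**The case against.** The strongest reply is that 135 can be reconciled with the plan. As a seasonal cumulative figure it fits household sizes 3 and 4, and as a person-year rate for primary cases it falls within 101–168. The 150 also equals B5's 15% expressed per 1,000, which suggests an origin, although the SAP does not state one. This stands, and it rules out a tempting stronger reading: that 135 flatly contradicts the 25% attack rate. The documents do not support that, because the answer depends on a unit they leave undefined. The reconciliation is not in the text either: the SAP speaks of an incidence rate among participants, not of primary cases or a seasonal risk.

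A reader might also infer that meeting the benchmark would still leave the ±0.12 precision out of reach. That is not established. At size 4, 135 per 1,000 person-years gives 67 infections among 1,000 people, against the 63 behind ±0.12, and 1.96 × 0.5/√67 = 0.12. At size 3 it gives about 50 (±0.14) and at size 5 about 84. If the 67 include secondary cases, only about 31 to 44 are first cases (67.3/2.14 and 67.3/1.54). The consequence therefore turns on which infections are counted.

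The fall from 150 to 120 is 20%, against 30% in the B5 conclusion. Little follows from that: B5 lists detectable effects, not expected ones, and a 30% fall would move the average only to (150 + 105)/2 = 127.5.

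Finally, the per-person-day value is so absurd that a DSMB would query it, no stopping rule hangs on the benchmark, and the check may never run. Protocol section IX has the DSMB meet only before enrolment and after the season, and section XI excludes an interim analysis. All of this limits the harm. It does not make the number right, and the conflict over meetings itself needs resolving.

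**Conclusion.** The point holds as an inconsistency of design and definition, not an arithmetic slip. The benchmark presupposes two study periods that neither design description contains, its unit is undefined, and it is not taken from the study's planning figures. Depending on the reading, 135 is impossible, about 46–78% of plan, compatible with plan, or at the top of plan for households of four. The validity check can therefore pass or fail on interpretation alone. A flat mismatch with the attack-rate table, or a demonstrated loss of precision, should not be claimed. The figures rest on full 182-day follow-up; later enrolment shortens person-time and, for the same case counts, raises the implied rates per unit of time. The correction should be made, and it is cheap.

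**What to change.** In SAP section C, delete the control-period and intervention-period rates and their average. Replace them with one benchmark for the single cohort in a defined unit taken from the planning table: 63 of 250 households with a first confirmed case by season end, expressed as 25% so that it scales if more households enrol. If an all-infection rate is preferred, give the matching figure with its assumed mean household size and secondary attack rate. Report beside it the number of participants in the primary-endpoint denominator (Protocol section III: drug eligible, and positive on both the self-test and the laboratory test), since that is narrower than the household count.

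Reconcile the SAP's monthly DSMB review with the Protocol's pre-season and post-season meetings and its statement on interim analysis. If interim looks at incidence are kept, expected counts by date need a stated, assumed seasonal profile, because neither document gives one.

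Remove the same leftover two-period text elsewhere in the SAP: the SAE comparison between periods in B4 and the Wald test between periods in B6. The cost is SAP wording and alignment with the Protocol; the counts come from results the study already plans to collect.

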Secondary aim: Determine the social and technical infrastructure that would be required to rapidly detect and interrupt influenza transmission at the household level and to determine whether a home-based self-test and antiviral delivery strategy would be feasible in the context of a pandemic.

Primary Objectives:

P1) To measure the proportion of individuals who are initiated on antiviral therapy within 48 hours of symptom onset using home-based self-test to diagnose influenza and home delivery of antivirals.

Secondary Objectives:

S1) Proportion of individuals who test positive for influenza using the home-based test within 48 hours of symptom onset

S2) Proportion of individuals who are delivered antivirals within 48 hours of symptom onset

S3) Symptom duration and severity among cases and household contacts

S4) Viral titer and duration of viral RNA detection among influenza-positive cases

S5) Cost effectiveness, assessed using health resource utilization and school and work absenteeism

S6) Emergence of antiviral resistance, assessed by genetic sequencing of influenza strains

B. Final Analysis Plan

This section describes the main statistical analyses that will be conducted on enrolled households at DSMB meetings and at the end of the study.

B1. Analysis Datasets

The Primary Dataset will consist of all individuals from enrolled households who enroll in the study, comprised of symptomatic (drug-eligible) individuals.

All eligible and enrolled households will be included in the study unless they meet one or more of the following exclusion criteria:

1. Previous documentation of an influenza infection prior to or during the annual influenza season in any household member prior to enrollment

At the participant level, enrolled individuals meeting any of the following criteria will be excluded from analysis (note: their household may still be eligible, as another eligible member of their household may still enroll):

1. The individual's informed consent is determined to be not valid
2. The individual has been double enrolled in the study. In this case, the individual's data will be used once.
3. No symptom questionnaire is collected.

B2. Variable definitions

[See Tables 1a-c for details]

B3. Baseline Tables and Study Conduct

Description of the main tables and statistical analyses

This section describes the main tables and statistical analyses. Metrics will be updated monthly and presented to the DSMB at each meeting.

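### SAP section C's 20% resistance halting rule has no defined numerator or denominator, would very likely stay silent in a planned season if read as all participants, and has no working review date under the protocol

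*SAP*

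**What the plan says.** SAP section C (Interim Analysis Plan, under baloxavir-resistant strain transmission) contains the only numeric stopping threshold in either document: in what it calls an unlikely event, if "the incidence of the transmission of baloxavir-resistant strains of flu exceeds 20% of study participants, the study will be halted". It gives no definition of a transmission and no definition of the participants.

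Two other SAP sections use different populations. B1 describes the primary dataset as "comprised of symptomatic (drug-eligible) individuals". For the resistance analysis, B4 states: "The unit of analysis will be influenza-positive tests".

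The planned amount of influenza is in the SAP B6 table, repeated in protocol section II. It gives primary and secondary cases in 250 households for household attack rates of 25%, 20% and 10%, with the note "Secondary attack rate 18-38%, secondary cases presented as a range based on these high and low bounds".

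On timing, SAP section C says "The DSMB will meet every month to review study progress and other issues as outlined below" and "Baloxavir resistance will be analyzed via interim analyses and monitored for the duration of the study". The SAP is dated October 2019. Protocol version 3.1, dated January 2020, says in section XI that there will be no interim analysis and that resistance will be reviewed when the season ends. Section IX schedules board meetings before pre-season enrollment and after the season. The protocol does not carry the 20% rule.

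**The concern.** A rule that requires a halt has to tell the monitoring board what to count, over whom, and when. This one leaves the first two open, and the two documents disagree on the third.

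The open denominator matters because influenza itself is uncommon among all household members. A threshold set as a share of everyone enrolled can exceed the total influenza expected, in which case it says almost nothing about resistance. The protocol (section VII) recognises that resistant strains could pass to people outside the study and that the likelihood is unknown. This rule is the SAP's numeric safeguard against that risk.

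**Working it through.** **Inputs.** SAP B6 table: 250 households; household attack rate 25% (its highest row); secondary attack rate 18-38%; mean household size 3, 4 or 5 including the case. Assumption: every household member enrols, giving 750, 1,000 or 1,250 participants.

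**Reproducing the table.** Primary cases = 250 × 0.25 = 62.5, shown as 63. Secondary cases = 63 × (size − 1) × 0.18 or 0.38, which gives 22.7-47.9, 34.0-71.8 and 45.4-95.8. The table prints 23-48, 34-72 and 45-96, so it reproduces.

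**Expected share on the all-participants reading, with every strain resistant.** Any strain = (63 + secondary) / participants. Transmitted only = secondary / participants.

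| Household size | Participants | Count needed (>20%) | Any strain | Transmitted only |
|---|---|---|---|---|
| 3 | 750 | more than 150 | 86-111 (11.5-14.8%) | 23-48 (3.1-6.4%) |
| 4 | 1,000 | more than 200 | 97-135 (9.7-13.5%) | 34-72 (3.4-7.2%) |
| 5 | 1,250 | more than 250 | 108-159 (8.6-12.7%) | 45-96 (3.6-7.7%) |

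The lower attack-rate rows give less: at most 88/750 = 11.7% at a 20% attack rate and 44/750 = 5.9% at 10%.

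**Chance of crossing 20% over the full season.** Each household has at most one introduction, with probability 0.25, and the secondary attack rate is 0.38. The exact distribution was summed over 250 households. The first figure takes secondary infections in a household as independent, the second as all-or-none.
- Size 3: 0.17% / 0.35%
- Size 4: 0.005% / 0.04%
- Size 5: 0.0002% / 0.01%
- Transmitted only, any size: effectively nil

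**Attack rate at which the expected share reaches 20%.** Solve h × [1 + 0.38(m − 1)] / m = 0.20 for household size m:
- m = 3: 0.60/1.76 = 34%
- m = 4: 0.80/2.14 = 37%
- m = 5: 1.00/2.52 = 40%

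**Other denominators.**
- Drug-eligible participants. Eligibility requires at least two per household. If there are exactly two (assumption), the denominator is 500, and the table's 86-159 infections are 17-32% of it. This is rough, because the numerator includes ineligible members, but it can pass 20%.
- Influenza-positive participants. The trigger is 13 or more resistant among 63, or 28 or more among 135. It fires on the resistant fraction whatever the size of the season.
- Symptomatic drug-eligible individuals, as in B1. The documents give no count, so nothing can be computed.

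**Schedules compared.** SAP: monthly board meetings and interim resistance analyses. Protocol: no interim analysis, resistance reviewed at season end, board meetings before enrollment and after the season. Neither document says which prevails.

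**The case against.** The SAP itself calls the event unlikely, so a remote backstop was intended, and silence at planned rates is not in itself a fault. That stands. But the phrase does not say which share is meant, and a trigger that would probably stay silent at 100% resistance is a weak guard against resistance.

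A reader might infer that the rule can never fire. The documents do not support that. The small probabilities hold the attack rate at 25%, and the SAP notes that incidence varies by season; at 34-40% the expected share reaches 20%. If only two members per household enrolled, the full-season chance would be 8.4%. Looks taken with few households cross more often: 7.8-17.8% with 20 households and 1.7-9.7% with 50 (sizes 3-5, any strain). These overstate the risk, because they give early households a full season's attack rate. Silence also depends on the all-participants reading.

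A reader might also seek support in the 15% transmission rate in SAP B5 or the expected event rate in section C. Neither has a clear unit, so neither can be set against a cumulative share of participants.

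On timing, each document does state a schedule, so the fault is a conflict between them. The protocol's general wording, that the board reviews data regularly and that resistance will be monitored, leaves in-season review possible but names no date.

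Finally, the board can stop the study on general safety grounds and adverse-event reporting continues. Baloxavir is one dose to one member per household. This limits the consequence but does not make the written rule usable.

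**Conclusion.** The point holds as a minor one. The missing definitions and the conflict in schedule are plain in the text.

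The finding that the rule would very likely stay silent is conditional. It rests on all enrolled household members being the denominator, full enrolment of each household, at most one introduction per household, and attack rates no higher than the plan's 25% and 38%. On those terms the chance of a halt over the season is 0.35% or less even if every strain is resistant. With drug-eligible or influenza-positive participants as the denominator, 20% could be crossed.

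On the meeting and review dates that the protocol names, the rule could not halt anything. The primary estimate, the proportion starting treatment within 48 hours, is not affected.

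**What to change.** In SAP section C:
- Define the numerator: all resistant infections, or transmitted ones only.
- State the trigger as a percentage of influenza-positive participants with a sequencing result, counting each participant once. This is close to B4 but not identical, since B4 counts tests.
- Apply it only after a minimum number of sequenced positives, for example 20, with level and minimum set by the sponsor and the monitoring board. The minimum matters. If true resistance is 5-10% (assumption), a rule of more than 20% of positives would halt at a single look with chance 18.5-34.4% at 4 positives (1 or more resistant), 1.2-7.0% at 10 (3 or more) and 0.3-4.3% at 20 (5 or more). At 50% true resistance it would still fire with chance 99.4% at 20.

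In both documents, state one schedule for resistance review and board meetings. If review is only at season end, remove the halting rule or say that it does not operate in season.

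The cost is mainly wording. If in-season review is kept, some sequencing results must be reviewed before the season ends, and the minimum count delays any halt until enough positives are sequenced.
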